3. **Target vessel non-fatal MI:** Only 1 of the trials identified reported the fatality rate of MI. In the RAVEL trial, the 3-year ratio of non-fatal MI to all MI was 0.75. We used this proportion for the other studies included in our analysis.
4. **TVF:** To match the TVF definition in the NIRTRAKS Post-Market Study, TVF was calculated as the sum of clinically driven TVR, target vessel non-fatal clinically relevant MI and cardiac death.
5. **TVF at 3 years:** In the ENDEAVOR II trial, 50% of the combined long-term outcome of death, MI and TVR occurred in the first 9 months post-procedure. For trials in which outcomes were reported for 4 or 5 years, we corrected the rates to 3 years by assuming that 50% of the events occurred during the first year, and the remainder were evenly distributed across the follow-up duration of years 2 to 5. Thus, the 3-year event rate was calculated according to the following formula:

$$\text{TVF}_3 = \text{TVF}_1 + \frac{\text{TVF}_n}{n - 1}$$

Where  $\text{TVF}_1 = 0.5 \cdot \text{TVF}_n$  and  $n$  = number of follow-up years reported in original publication.

We performed a random effects meta-analysis of the 3-year TVF rates from the BMS arms of included studies, following the approach in DerSimonian and Laird (1986). Based upon our analysis, the endpoint rate of TVF derived from the meta-analysis is **23.2%** (95% CI 19.8%, 26.7%).

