4.1 Sample Size Determination

Per agreement with the FDA (FDA decision letter dated 2017 February 10, following review of supplement P110004/S021), a sample size of 65 subjects was deemed adequate to provide sufficient information about the study device. By accounting for approximately 7.0% loss to follow-up per-year, approximately 52 evaluable subjects will be available for analysis after 3 years.

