4.3.2 Analysis of Primary Endpoint

The primary endpoint for this study is TVF, which is defined as a composite of cardiac death, target vessel MI, or clinically driven TVR by percutaneous or surgical methods within 3 years post-procedure.

No formal statistical test will be performed, as this study is descriptive only. The TVF rate at 3 years and the exact two-sided 95% confidence intervals will be provided. In addition, the TVF at 3 years will be estimated for all ITT subjects by generating the two-sided 95% confidence

interval of the Kaplan-Meier estimate of the primary endpoint rate; subjects not experiencing the endpoint will be censored at 3 years post-procedure or day of withdrawal, whichever is earlier. Finally, the same analysis will be carried out on the PP population (secondary analysis).

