4.3.3 Analysis of Secondary Endpoints

All secondary endpoints (listed below) are dichotomous variables. Secondary endpoints will be presented as the number and percentage of subjects experiencing the outcome, along with two-sided exact 95% confidence intervals of the percentages. Included in the denominators for each outcome will be patients experiencing the event within the period (e.g., 30 days for 30-day time point, 270 days for 9-month time point, 365 days for 1-year time point, 730 days for 2-year time point, and 1095 days for 3-year time point) or who have adequate follow-up (e.g., at least 16 days for 1-month time point, at least 240 days for the 9-month time point, at least 335 days for the 1-year time point, at least 700 days for 2-year time point, and at least 1065 days for 3-year time point).

In addition, a Kaplan-Meier (K-M) estimate of the event-free survival rate and its corresponding standard error will be presented for cardiac death, target vessel MI, clinically driven TLR and TVR, with a corresponding K-M curve.

The secondary endpoints that will be reported are as follows:

1. **TVF** at 9 Months.
2. **All cause death** at 30 days, and 1, 2 and 3 years.
3. **Cardiac death** at 30 days, and 1, 2 and 3 years.
4. **All cause MI** at 30 days, and 1, 2 and 3 years.
5. **Target vessel MI** at 30 days, and 1, 2 and 3 years.
6. **Clinically driven TLR** at 30 days, and 1, 2 and 3 years.
7. **Clinically driven TVR** at 30 days, and 1, 2 and 3 years.
8. **Acute success rates**

Device success: Attainment of <50% final residual stenosis of the target lesion using the NIRxcell Stent System only.

Lesion success: Attainment of <50% final residual stenosis of the target lesion using any percutaneous method.

Procedure success: Attainment of <50% residual stenosis of the target lesion and no in-hospital death, MI or TLR.

9. **Stent thrombosis** at hospital discharge, at 30 days, and 1, 2 and 3 years.

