4.4 Adverse Events

A Treatment Emergent Adverse Event (TEAE) is an event that emerges, or a pre-existing event that worsens, any time during or after stent implantation. Adverse events will be coded by the MedDRA system version 18.1 or later. The per-event and per-patient incidence of TEAEs will be presented overall and by MedDRA system organ class and preferred term. This will be repeated for serious TEAEs.

5 TABLES, FIGURES, and LISTINGS

Table 1.1a Primary Endpoints – Intention-to-Treat Analysis Set

Primary Endpoint	ITT Subjects with Available Data (N=xx subjects)	Two-sided Binomial Exact 95% CI
TVF at 3 years	xx.xx% (xx/xx)	[xx.xx%, xx.xx%]
Cardiac Death	xx.xx% (xx/xx)	[xx.xx%, xx.xx%]
Target Vessel MI	xx.xx% (xx/xx)	[xx.xx%, xx.xx%]
Clinically-driven TVR	xx.xx% (xx/xx)	[xx.xx%, xx.xx%]

Note: Events defined for the period of 3 year post-procedure follow up are reported for patients with at least 1050 days of follow-up or with event to 3 years (1080 days).

Table 1.1b Primary Endpoints – Per-Protocol Analysis Set

Table 1.2 Secondary Endpoints – Intention-to-Treat Analysis Set

	ITT Subjects (N=xx subjects)	Two-sided Binomial Exact 95% CI
TVF at 9 months	xx.xx% (xx/xx)	[xx.xx%, xx.xx%]
All Cause Death		
30-day	xx.xx% (xx/xx)	[xx.xx%, xx.xx%]
1-year	xx.xx% (xx/xx)	[xx.xx%, xx.xx%]
2-year	xx.xx% (xx/xx)	[xx.xx%, xx.xx%]
3-year	xx.xx% (xx/xx)	[xx.xx%, xx.xx%]
Cardiac Death		
30-day	xx.xx% (xx/xx)	[xx.xx%, xx.xx%]
1-year	xx.xx% (xx/xx)	[xx.xx%, xx.xx%]
2-year	xx.xx% (xx/xx)	[xx.xx%, xx.xx%]
3-year	xx.xx% (xx/xx)	[xx.xx%, xx.xx%]
All Cause MI		
30-day	xx.xx% (xx/xx)	[xx.xx%, xx.xx%]
1-year	xx.xx% (xx/xx)	[xx.xx%, xx.xx%]
2-year	xx.xx% (xx/xx)	[xx.xx%, xx.xx%]
3-year	xx.xx% (xx/xx)	[xx.xx%, xx.xx%]
Target Vessel MI		
30-day	xx.xx% (xx/xx)	[xx.xx%, xx.xx%]
1-year	xx.xx% (xx/xx)	[xx.xx%, xx.xx%]
2-year	xx.xx% (xx/xx)	[xx.xx%, xx.xx%]
3-year	xx.xx% (xx/xx)	[xx.xx%, xx.xx%]
Clinically-driven TLR		
30-day	xx.xx% (xx/xx)	[xx.xx%, xx.xx%]
1-year	xx.xx% (xx/xx)	[xx.xx%, xx.xx%]
2-year	xx.xx% (xx/xx)	[xx.xx%, xx.xx%]
3-year	xx.xx% (xx/xx)	[xx.xx%, xx.xx%]
Clinically-driven TVR		
30-day	xx.xx% (xx/xx)	[xx.xx%, xx.xx%]

1-year	xx.xx% (xx/xx)	[xx.xx%, xx.xx%]
2-year	xx.xx% (xx/xx)	[xx.xx%, xx.xx%]
3-year	xx.xx% (xx/xx)	[xx.xx%, xx.xx%]
Device Success ¹	xx.xx% (xx/xx)	[xx.xx%, xx.xx%]
Lesion Success ²	xx.xx% (xx/xx)	[xx.xx%, xx.xx%]
Procedure Success ³	xx.xx% (xx/xx)	[xx.xx%, xx.xx%]
Stent Thrombosis		
Discharge	xx.xx% (xx/xx)	[xx.xx%, xx.xx%]

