30-day	xx.xx% (xx/xx)	[xx.xx%, xx.xx%]
1-year	xx.xx% (xx/xx)	[xx.xx%, xx.xx%]
2-year	xx.xx% (xx/xx)	[xx.xx%, xx.xx%]
3-year	xx.xx% (xx/xx)	[xx.xx%, xx.xx%]

1 Device success is defined as attainment of <50% final residual stenosis of the target lesion using only the NIRxcell Stent System.

2 Lesion success is defined as attainment of <50% final residual stenosis of the target lesion using any percutaneous method.

3 Procedure success is defined as attainment of <50% residual stenosis of the target lesion and no in-hospital death, MI, or TLR.

Events in this table have been adjudicated by the CEC.

Denominators for 30-day events will reflect the number of patients with an adjudicated event in 30 days or follow-up through 16 days.

Denominators for 9-month events will reflect the number of patients with an adjudicated event in 270 days or follow-up through 240 days.

Denominators for 1-year events will reflect the number of patients with an adjudicated event in 365 days or follow-up through 335 days.

Denominators for 2-year events will reflect the number of patients with an adjudicated event in 730 days or follow-up through 700 days.

Denominators for 3-year events will reflect the number of patients with an adjudicated event in 1095 days or follow-up through 1065 days.

Table 2 Enrollment by Site

Site	Site Name	Site Location	ITT Subjects (N=xx subjects)	Per Protocol Subjects (N=xx subjects)
001			xx	xx
002			xx	xx
Total			xx	xx

Table 3 Compliance Table -- Intention-to-Treat Analysis Set

Site	Index Procedure Form	30-Day Contact ¹	9-Month Contact ²	1-Year Contact ³	2-Year Contact ⁴	3-Year Contact ⁵
	(received/expected, %)	(received/expected, %)	(received/expected, %)	(received/expected, %)	(received/expected, %)	(received/expected, %)
001	xx.xx% (xx/xx)	xx.xx% (xx/xx)	xx.xx% (xx/xx)	xx.xx% (xx/xx)	xx.xx% (xx/xx)	xx.xx% (xx/xx)
002	xx.xx% (xx/xx)	xx.xx% (xx/xx)	xx.xx% (xx/xx)	xx.xx% (xx/xx)	xx.xx% (xx/xx)	xx.xx% (xx/xx)
...
014						
015						
Total	xx.xx% (xx/xx)	xx.xx% (xx/xx)	xx.xx% (xx/xx)	xx.xx% (xx/xx)	xx.xx% (xx/xx)	xx.xx% (xx/xx)

1 Denominator for 30-Day contact includes patients who had 30-day visit form filled or patients who have reached 44 (30+14) days after procedure (data export date - procedure date) and excludes patients who died or withdrew before 44 days.

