2 Denominator for 9-Month contact includes patients who had 9-month visit form filled or patients who have reached 300 (270+30) days after procedure (data export date - procedure date) and excludes patients who died or withdrew before 300 days.

3 Denominator for 1-year contact includes patients who had 1-year visit form filled or patients who have reached 395 (365+30) days after procedure (data export date - procedure date) and excludes patients who died or withdrew before 395 days.

4 Denominator for 2-year contact includes patients who had 2-year visit form filled or patients who have reached 760 (730+30) days after procedure (data export date - procedure date) and excludes patients who died or withdrew before 760 days.

5 Denominator for 3-year contact includes patients who had 3-year visit form filled or patients who have reached 1125 (1095+30) days after procedure (data export date - procedure date) and excludes patients who died or withdrew before 1125 days.

Table 4 Patient Disposition

	ITT Subjects (N=xx subjects)	Per Protocol Subjects (N=xx subjects)
	n (%)	n (%)
Enrolled	xx (xx.xx%)	xx (xx.xx%)
Completed the study	xx (xx.xx%)	xx (xx.xx%)
Not completed all required follow-up visits	xx (xx.xx%)	xx (xx.xx%)
Primary reason for not completed		
Withdrew consent	xx (xx.xx%)	xx (xx.xx%)
Lost to follow-up	xx (xx.xx%)	xx (xx.xx%)
Adverse event	xx (xx.xx%)	xx (xx.xx%)
Death	xx (xx.xx%)	xx (xx.xx%)
Lack of efficacy	xx (xx.xx%)	xx (xx.xx%)
Protocol violation	xx (xx.xx%)	xx (xx.xx%)
Physician decision	xx (xx.xx%)	xx (xx.xx%)
Study cancelled	xx (xx.xx%)	xx (xx.xx%)
Other	xx (xx.xx%)	xx (xx.xx%)

Table 5 Demographic and Medical History – Intention-to-Treat Analysis Set

Characteristics	ITT Subjects (N=xx subjects)	95% CI
Demographics		
Age (yrs)		
Mean±SD (N)	xx.xx±xx.xx (xx)	[xx.xx, xx.xx]
Median (Q1, Q3)	xx.xx (xx.xx, xx.xx)	
Range (min, max)	(xx.xx, xx.xx)	
Male	xx.xx% (xx/xx)	[xx.xx%, xx.xx%]
Ethnicity		
Hispanic or Latino	xx.xx% (xx/xx)	[xx.xx%, xx.xx%]
Not Hispanic or Latino	xx.xx% (xx/xx)	[xx.xx%, xx.xx%]
Race		
American Indian or Alaska Native	xx.xx% (xx/xx)	[xx.xx%, xx.xx%]
Asian	xx.xx% (xx/xx)	[xx.xx%, xx.xx%]
Black or African American	xx.xx% (xx/xx)	[xx.xx%, xx.xx%]
Native Hawaiian or Other Pacific Islander	xx.xx% (xx/xx)	[xx.xx%, xx.xx%]
White	xx.xx% (xx/xx)	[xx.xx%, xx.xx%]
Other	xx.xx% (xx/xx)	[xx.xx%, xx.xx%]
Medical History/Risk Factor		
Previous MI	xx.xx% (xx/xx)	[xx.xx%, xx.xx%]
Previous PCI	xx.xx% (xx/xx)	[xx.xx%, xx.xx%]

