
	ITT Subjects (N=xx subjects)	95% CI
Thrombus	xx.xx% (xx/xx)	[xx.xx%, xx.xx%]
Aneurysm	xx.xx% (xx/xx)	[xx.xx%, xx.xx%]
Final TIMI		
0	xx.xx% (xx/xx)	[xx.xx%, xx.xx%]
1	xx.xx% (xx/xx)	[xx.xx%, xx.xx%]
2	xx.xx% (xx/xx)	[xx.xx%, xx.xx%]
3	xx.xx% (xx/xx)	[xx.xx%, xx.xx%]
No Reflow	xx.xx% (xx/xx)	[xx.xx%, xx.xx%]
Abrupt Closure	xx.xx% (xx/xx)	[xx.xx%, xx.xx%]
Spasm	xx.xx% (xx/xx)	[xx.xx%, xx.xx%]
Dissection		
0	xx.xx% (xx/xx)	[xx.xx%, xx.xx%]
A	xx.xx% (xx/xx)	[xx.xx%, xx.xx%]
B	xx.xx% (xx/xx)	[xx.xx%, xx.xx%]
C	xx.xx% (xx/xx)	[xx.xx%, xx.xx%]
D	xx.xx% (xx/xx)	[xx.xx%, xx.xx%]
E	xx.xx% (xx/xx)	[xx.xx%, xx.xx%]
F	xx.xx% (xx/xx)	[xx.xx%, xx.xx%]
Staining	xx.xx% (xx/xx)	[xx.xx%, xx.xx%]
Distal Embolism	xx.xx% (xx/xx)	[xx.xx%, xx.xx%]
Perforation	xx.xx% (xx/xx)	[xx.xx%, xx.xx%]
Branch % Diameter Stenosis		
Mean±SD (N)	xx.xx±xx.xx (xx)	[xx.xx, xx.xx]
Median (Q1, Q3)	xx.xx (xx.xx, xx.xx)	
Range (min, max)	(xx.xx, xx.xx)	

Data presented in this table is from the Angiographic Core Laboratory.

**Table 11a Combined In and Out-of-Hospital Complications to xx days–
Intention-to-Treat Analysis Set**

	ITT Subjects (N=xx subjects)	95% CI
To 30-day		
TVF (Cardiac death, Target Vessel MI, and Clinically-driven TVR)	xx.xx% (xx/xx)	[xx.xx%, xx.xx%]
Death	xx.xx% (xx/xx)	[xx.xx%, xx.xx%]
Cardiac Death	xx.xx% (xx/xx)	[xx.xx%, xx.xx%]
Non-Cardiac Death	xx.xx% (xx/xx)	[xx.xx%, xx.xx%]
All Cause MI (ARC)	xx.xx% (xx/xx)	[xx.xx%, xx.xx%]
Peri-Procedural PCI		
Peri-Procedural CABG	xx.xx% (xx/xx)	[xx.xx%, xx.xx%]
Spontaneous	xx.xx% (xx/xx)	[xx.xx%, xx.xx%]
Silent	xx.xx% (xx/xx)	[xx.xx%, xx.xx%]
Sudden Death	xx.xx% (xx/xx)	[xx.xx%, xx.xx%]
Reinfarction	xx.xx% (xx/xx)	[xx.xx%, xx.xx%]
Q wave MI	xx.xx% (xx/xx)	[xx.xx%, xx.xx%]
Non-Q wave MI	xx.xx% (xx/xx)	[xx.xx%, xx.xx%]
Target Vessel MI	xx.xx% (xx/xx)	[xx.xx%, xx.xx%]
Target Vessel Q wave MI	xx.xx% (xx/xx)	[xx.xx%, xx.xx%]
Target Vessel Non-Q wave MI	xx.xx% (xx/xx)	[xx.xx%, xx.xx%]
Non-Target Vessel MI	xx.xx% (xx/xx)	[xx.xx%, xx.xx%]
Non-Target Vessel Q wave MI	xx.xx% (xx/xx)	[xx.xx%, xx.xx%]
Non-Target Vessel Non-Q wave MI	xx.xx% (xx/xx)	[xx.xx%, xx.xx%]
All Revascularization	xx.xx% (xx/xx)	[xx.xx%, xx.xx%]
PCI	xx.xx% (xx/xx)	[xx.xx%, xx.xx%]
CABG	xx.xx% (xx/xx)	[xx.xx%, xx.xx%]
Clinically-driven Revascularization	xx.xx% (xx/xx)	[xx.xx%, xx.xx%]
PCI	xx.xx% (xx/xx)	[xx.xx%, xx.xx%]

CABG	xx.xx% (xx/xx)	[xx.xx%, xx.xx%]
Non-Clinically-driven Revascularization	xx.xx% (xx/xx)	[xx.xx%, xx.xx%]
PCI	xx.xx% (xx/xx)	[xx.xx%, xx.xx%]

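### The primary endpoint table ends 3 years at day 1080 (at least 1050 days of follow-up), while the rest of the SAP uses 1095 and 1065 days, so 3-year TVF can be reported with two values

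*SAP*

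**What the plan says.** **Primary endpoint.** SAP 4.3.2 defines TVF as an event within 3 years of the procedure. It asks for the 3-year rate with an exact two-sided 95% interval, plus a Kaplan-Meier estimate in which event-free subjects are "censored at 3 years post-procedure or day of withdrawal, whichever is earlier". It does not say how many days 3 years is. The note under Table 1.1a supplies the number: the table covers patients "with at least 1050 days of follow-up or with event to 3 years (1080 days"). Table 1.1b (per-protocol) has a title but no note of its own.

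**Everything else at 3 years.** SAP 4.3.3 counts secondary events up to 1095 days and otherwise requires "at least 1065 days for 3-year time point". The notes to Tables 1.2 and 11a repeat this: "Denominators for 3-year events will reflect the number of patients with an adjudicated event in 1095 days or follow-up through 1065 days". Table 3, on contact compliance, also starts from 1095 days: "patients who have reached 1125 (1095+30) days after procedure".

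**Where the same outcomes are printed twice.** Table 1.1a shows TVF and its three components. Table 1.2 shows the three components at 3 years, but TVF only at 9 months. Table 11a opens with a TVF row, "TVF (Cardiac death, Target Vessel MI, and Clinically-driven TVR"), and ends with a heading for the 3-year block.

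**The concern.** The primary table and the other 3-year tables use different definitions of 3 years, and both stand in the current SAP (version 3.2). The 1080/1050 pair fits the 3-year window that the document history says was replaced in version 3.1 (1080 ± 30 days became 1095 ± 30). The note was therefore probably missed in that update. The conflict does not depend on the history, because it lies between the Table 1.1a note and the current text of 4.3.3 and Tables 1.2, 3 and 11a.

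A programmer who follows the shells as written would compute the headline rate under one rule and every other 3-year rate under another. The study is now descriptive, so the 3-year TVF rate and its interval are the main result. That figure should not depend on which table note is read, and the rule should not be chosen after the data are seen.

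**Working it through.** **1. Size of the gap**

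| | Table 1.1a note | 4.3.3, Tables 1.2 and 11a | Difference |
|---|---|---|---|
| Last day an event counts | 1080 | 1095 | 15 days |
| Minimum follow-up if event-free | 1050 | 1065 | 15 days |

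**2. Who is treated differently**

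- A first TVF event on days 1081-1095 is not an event by 3 years under the Table 1.1a rule, but is one under the Table 11a rule. The subject is in both denominators.
- An event-free subject last followed on days 1050-1064 is in the Table 1.1a denominator and not in the other.
- Both differences lower the rate in the primary table, so they cannot offset each other.

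**3. Number of subjects (SAP 4.1)**

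The SAP expects "approximately 52 evaluable subjects will be available for analysis after 3 years". With 65 enrolled and 7.0% loss per year, 65 × 0.93³ = 52.3, so its figure is reproduced.

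**4. Chance of an event on days 1081-1095**

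The expected 3-year TVF rate is 23.2% (protocol 12.2). Timing comes from protocol 12.1, which rescales 4- and 5-year trial data by "assuming that 50% of the events occurred during the first year" and spreading the rest evenly: TVF₃ = 0.5·TVFₙ + TVFₙ/(n − 1).

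- n = 5: TVF₃ = 0.75·TVF₅, so the year-1 share of 3-year events is 0.5/0.75 = 66.7%.
- n = 4: TVF₃ = 0.833·TVF₄, so the share is 0.5/0.833 = 60%.

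| Share of 3-year events in years 2-3 | Rate per year | Over 15 days (× 15/365) | Expected events in 52 | Chance of at least one, 1 − exp(−x) |
|---|---|---|---|---|
| 33.3% (n = 5) | 0.232 × 0.333/2 = 3.87% | 0.159% | 0.083 | 7.9% |
| 40% (n = 4) | 0.232 × 0.40/2 = 4.64% | 0.191% | 0.099 | 9.4% |
| 50% (assumption) | 0.232 × 0.50/2 = 5.80% | 0.238% | 0.124 | 11.7% |

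Using all 65 enrolled in place of 52, the first and last rows become 0.103 and 0.155 expected events, or 10% and 14%.

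**5. Chance of follow-up ending on days 1050-1064**

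Assume the 7% annual loss is spread evenly over time. Then 65 × 0.93^(1050/365) × (1 − 0.93^(15/365)) = 0.157 expected withdrawals, about a 15% chance of at least one. This counts all subjects, including any who already had an event, so it overstates the number that matters.

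**6. Effect on the reported rate (exact 95% intervals)**

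Take 12 events by day 1080 among 52 subjects as the illustration.

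| Situation | Rate | Exact 95% CI |
|---|---|---|
| Table 1.1a rule | 12/52 = 23.1% | 12.5-36.8% |
| Table 11a rule, one event on days 1081-1095 | 13/52 = 25.0% | 14.0-38.9% |
| Table 11a rule, one event-free subject last followed on days 1050-1064 | 12/51 = 23.5% | 12.8-37.5% |
| Table 11a rule, both | 13/51 = 25.5% | 14.3-39.6% |

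One event in the gap is worth 1.9 percentage points. One early-ending subject is worth about 0.45.

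**The case against.** **The effect is small.** No test is planned, the likeliest outcome is that no event falls in the gap, and a 1.9-point shift sits inside an interval about 24 points wide. This is correct.

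**The 23.2% may be too high.** The protocol's introduction gives a 270-day TVF of 8.7% for the predecessor system, which uses the same stent. Treating that as 60-67% of the 3-year total (an assumption) gives 3-year TVF of 8.7/0.667 = 13.0% to 8.7/0.60 = 14.5%. Expected gap events are then 0.05-0.06, a chance of about 5-6%. So the 8-12% depends on the protocol's own rate.

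**The note may govern only who is counted.** A subject with a first event on day 1085 already has more than 1050 days of follow-up and is in the table. The note does not say in terms that the event is ignored. That reading is possible, but the note equates 3 years with 1080 days and no other primary-endpoint text gives a different number. Even on that reading, the denominators still differ.

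**Last follow-up on days 1050-1064 is unlikely.** Scheduled contacts are annual, so last contacts may cluster near year 2 and the even-loss figure may be too high. This is also fair.

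**The duplication is partly inferred.** Table 1.2 has no 3-year TVF row, and the 3-year block of Table 11a is an empty heading whose rows are evidently meant to repeat. For cardiac death, target vessel MI and clinically driven TVR no inference is needed: Tables 1.1a and 1.2 both print them at 3 years.

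**Two 3-year estimates are planned anyway.** The binomial and Kaplan-Meier estimates will differ for a stated methodological reason. Two binomial rates for the same outcome in the same population should not.

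**Figure 2 is weak evidence.** Its printed bins end at day 1080, but its title leaves the day open.

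**Conclusion.** The concern holds. The current SAP gives two day-level definitions of 3 years. The one attached to the primary endpoint table disagrees with every other 3-year analysis rule, and 4.3.2 does not settle it. Followed as written, the plan can give 3-year TVF one value in Table 1.1a and a higher one in Table 11a. Its three components can likewise differ between Table 1.1a and Tables 1.2 and 11a.

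The expected effect is small: roughly an 8-12% chance of an event in the gap, worth 1.9 points if there is one, and about 0.45 points for each early-ending event-free subject. These figures rest on 23.2% TVF at 3 years, about 52 evaluable subjects and evenly spread late events. No hypothesis test or threshold is affected. It should still be corrected, because it is a wrong rule for the main result and almost free to fix.

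**What to change.** - In the Table 1.1a note, change 1050 to 1065 and 1080 to 1095. Print the same note under Table 1.1b.
- In SAP 4.3.2, add one sentence: for the binomial rate, 3 years means an event by day 1095 or at least 1065 days of follow-up; for the Kaplan-Meier estimate, event-free subjects are censored at day 1095 or at withdrawal if earlier.
- Extend the Figure 2 axis and at-risk table to day 1095.

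The cost is two numbers in a table note, one sentence and the last bin of a figure. No new data are needed. If the tables have already been produced, rerun Tables 1.1a and 1.1b under the corrected rule and say whether any subject fell in either 15-day gap.

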# At Risk							
# Censored							
# Events							
% Survived							
SE							

0 180 360 540 720 900 1080

**Figure 3 Kaplan-Meier Survival from Stent Thrombosis from Procedure
to xx Days – Intention-to-Treat Analysis Set**
